##### **4.2.6.7.1 Weight**

On top of listing the data as mentioned in section 4.2.6.7 above, the summary table presenting the actual (absolute) values and change from baseline to Week 12 will be prepared.

#### **4.2.6.8 Neurological examination findings**

A summary of the overall assessments across all neurological evaluations will be provided by treatment arms for each visit.

In addition, a key participant information table will be produced summarising data of all participants with at least one reported abnormality.

#### **4.2.6.9 Total neuropathy score-nurse (TNSn) results**

A summary of the total neuropathy score – nurse (TNSn) results will be prepared, including results for each of the following categories:

- Sensory symptom score
- Motor symptom score
- Autonomic symptom score
- Pin sensibility score
- Vibration sensibility score
- TNSn total

#### **4.2.6.10 Injection site reaction**

An incidence summary by severity (mild, moderate, severe) or presence (yes, no) and visit/timepoint will be prepared for the following injection site reactions:

- Pain (mild, moderate, severe)

- Tenderness (mild, moderate, severe)
- Erythema/redness (mild, moderate, severe)
- Induration/swelling (mild, moderate, severe)
- Necrosis (mild, moderate, severe)
- Ulceration (yes, no)

In addition, the quantitative result for erythema/redness and induration/swelling measurements (cm) will be summarised descriptively by visit/timepoint.

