### **3.6.1.1 Adverse events of special interest**

An AE of special interest (AESI) is one of scientific and medical interest specific to understanding of the IP and may require close monitoring and collecting additional information by the investigator. An AESI may be serious or nonserious. The rapid reporting of AESIs allows ongoing surveillance of these events to characterise and understand them in association with the use of MEDI7352.

AESIs for MEDI7352 include, but are not limited to:

- Positively-adjudicated possible or probable Rapidly Progressive Osteoarthritis (RPOA), Subchondral Insufficiency Fracture (SIF), primary osteonecrosis, or pathological fracture
- Infections that meet SAE or severe AE criteria (see CSP Appendix C 2)
- Anaphylactic reactions; serious or severe hypersensitivity reactions; or injection site reactions that lead to permanent discontinuation of administration of IP
- Other – includes AESIs that do not meet any of the above criteria, but are deemed of interest by the study team

AESIs irrespective of their severity and seriousness should be reported immediately using the same procedure as for SAE reporting (See CSP section 8.3.9).

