##### **4.2.6.1 Adverse Events**

Summary tables will include TEAEs as defined in section 3.6.1, unless otherwise specified.

An AE overview summary table will be produced showing the number (%) of participants with at least one AE in each of the following categories:

- Any AE
- Any AE with an outcome of death
- Any SAE

- Any AE leading to discontinuation of study treatment
- Any severe AE
- Any AESI
- Any AE leading to withdrawal from study

For all categories above, the number (%) of participants with at least one causally related AE in that category will also be provided.

An additional table will be produced showing the incidence of participants with the following type of adjudicated events:

- RPOA (type 1 and 2)
- SIF
- Primary osteonecrosis,
- Pathological fracture

The number of participants treated per treatment group will be used as the denominator to calculate percentages.

Summary tables will be produced by MedDRA SOC and PT for the following categories:

- AEs
  - By age group as defined in section 4.2.8
  - By sex
  - By periods as defined in section 3.1.6.
  - By ADA categories as defined in section 3.4.2
- Severe AEs
- By periods as defined in section 3.1.6. Causally related AEs and SAEs
  - By periods as defined in section 3.1.6.
- SAEs with outcome death
- SAEs
  - By periods as defined in section 3.1.6.
  - By ADA categories as defined in section 3.4.2
- AEs leading to discontinuation of study treatment
- AESIs
  - By periods as defined in section 3.1.6
  - Separate table to be provided for each AESI category as defined in section 3.6.1.1
    - By periods as defined in section 3.1.6
    - Joint related AESI table by study periods will also include the exposure adjusted rates, where AE event rate (per 100 participant years) is defined as the number of

participants with that AE divided by the total number of days at risk for AEs across all participants in given treatment arm and multiplied by  $365.25 \times 100$  to present in terms of per 100 participant years.

- Most common non-serious AEs defined as AEs occurring in at least 5% of participants overall (in total column). For each SOC/PT, the number (%) of participants reporting at least one event at each level of summarisation will be presented. Participants with multiple occurrences of the same AE, the event will only be counted once per SOC/PT. Those will be sorted by international order for system organ class and in alphabetical order for preferred term.

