In addition, a table with AEs and event counts sorted by decreasing frequency on preferred term will be produced as well as AEs by maximum intensity on preferred term by SOC and PT.

Additional table presenting mapping of AESIs will be produced.

A separate table with key participant information will be produced for:

- SAEs with outcome of death
- SAEs
- AEs leading to discontinuation of study treatment

A separate listing will be produced for the following AE categories:

- AEs
- SAEs
- AESIs
- AEs leading to discontinuation of study treatment

For any AE with change in intensity, listings will report all intensities as well as associated actions.

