#### 4.2.6.5 Vital signs results

Table with descriptive summaries (n, mean, SD, median, minimum, maximum, Q1 and Q3) of observed values and changes from baseline values for each treatment group at each protocol scheduled time point will be produced for the following vital signs tests:

- Systolic BP
- Diastolic BP
- Pulse rate
- Respiratory rate
- Temperature

In addition, shift table from baseline to minimum/maximum value during treatment will be produced for all above mentioned parameters. The reference ranges provided in section 3.6.5 will be used to determine whether the minimum/maximum value during treatment is within the normal range or not.

A by-visit incidence summary of orthostatic hypotension will be prepared for the following result categories:

- Criteria met
- Confirmed
- Symptomatic

A table presenting the changes in postural BP at each timepoint/ visit will be produced. Consequently, the supine readings from VS (for non-dosing visits) and VS1 (for dosing visits) eCRF forms as well as postural readings from VS2 eCRF form will be summarised descriptively by cohorts at each visit and all available timepoints as per all three eCRF forms. In addition, a listing of confirmed and symptomatic orthostatic hypotension cases will be prepared. The listing will include all participants with at least one assessment indicated as a confirmed or symptomatic case of orthostatic hypotension. All available results will be presented in order to see the change over time.

Vital signs data for participants/parameter with at least one abnormal result for the below mentioned parameters will be listed:

- Systolic BP (Including assessments from VS2 page in the eCRF)
- Diastolic BP (Including assessments from VS2 page in the eCRF)
- Pulse rate
- Respiratory rate
- Temperature

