- Provided that the ECG evaluations are performed locally by sites, only the abnormal evaluations will be listed.
- Given that TNSn and Injection site reactions data are tabulated, the listings were not generated.

- An additional AESI category was defined in this SAP that does not feature in the protocol. This category was classed as ‘Other AESIs’ and has been defined as any other AEs that are deemed of an interest by the study team.

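### Graded injection-site reactions are tabulated only by visit and their listing is dropped, so no specified output of these data gives participants ever affected, or their worst severity, per arm

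*SAP*

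**What the plan says.** Section 4.2.6.10 of the SAP defines the injection-site table: "An incidence summary by severity (mild, moderate, severe) or presence (yes, no) and visit/timepoint will be prepared for the following injection site reactions". Six reaction types follow. Five are graded mild, moderate or severe, and ulceration is recorded as present or absent. The size data follow the same layout, since the erythema and induration "measurements (cm) will be summarised descriptively by visit/timepoint". No row across visits and no worst-grade row is specified.

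Section 6 adds: "Given that TNSn and Injection site reactions data are tabulated, the listings were not generated".

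Other outputs bear on the question:

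- Section 4.2.6.1 plans AE tables at participant level. Its item on the most common non-serious AEs states: "Participants with multiple occurrences of the same AE, the event will only be counted once per SOC/PT". It also plans a table of "AEs by maximum intensity on preferred term by SOC and PT".
- Section 3.6.1.1 names as AEs of special interest (AESIs) those "injection site reactions that lead to permanent discontinuation of administration of IP". Section 4.2.6.1 gives each AESI category its own table.
- For orthostatic hypotension, section 4.2.6.5 says: "A by-visit incidence summary of orthostatic hypotension will be prepared for the following result categories". The categories are criteria met, confirmed and symptomatic. The same section keeps a listing: "The listing will include all participants with at least one assessment indicated as a confirmed or symptomatic case of orthostatic hypotension".

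**The concern.** Section 1.1.3 names injection-site reactions among the safety endpoints, and the product is injected six times. When doses are compared on local tolerability, the natural questions are how many participants per arm ever had a reaction and how severe their worst one was. A by-visit table answers neither. It gives the share reacting at each injection, but not whether the same people react each time.

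The reason given for dropping the listing does not hold for these data. The table does not contain what the listing would have preserved, namely the link between a participant's repeated assessments. Two arms with identical by-visit rows could differ several-fold in the number of participants affected.

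**Working it through.** No figure in the SAP bears on this point, so there is nothing to reproduce. The check has two parts.

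**1. Which planned output could give a per-arm count of participants ever affected?**

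| Output | Participants ever affected? | Worst severity? |
|---|---|---|
| Injection-site table (4.2.6.10) | No, by visit only | No |
| Injection-site size data (4.2.6.10) | No, by visit only | No |
| Injection-site listing | Dropped (section 6) | Dropped |
| AE tables by SOC and PT, maximum-intensity table (4.2.6.1) | Yes, if recorded as an AE | Yes, if recorded as an AE |
| AESI table | Only reactions leading to permanent discontinuation | Not specified |

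Section 3.6.9 describes a separate graded local assessment. Section 3.6.1.2 provides for AEs that are reported, elicited or observed to be recorded. Nothing in the SAP says that every graded local reaction is also entered as an AE.

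**2. How loosely do by-visit rates fix the number ever affected?**

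Inputs from the SAP: about 350 randomised (section 1.3), five arms in equal allocation and six injections (section 1.2). That gives 350 / 5 = 70 per arm. The per-visit rate *p* is an assumption, taken as equal at every injection with all participants assessed each time.

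- Lowest possible share ever affected (always the same people): *p*
- Independent between injections: 1 − (1 − *p*)^6
- Highest possible (different people each time): 6*p*

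| Assumed *p* | Same people | Independent | All different |
|---|---|---|---|
| 2% | 2% (1.4 of 70) | 11.4% (8.0 of 70) | 12% (8.4 of 70) |
| 5% | 5% (3.5 of 70) | 26.5% (18.5 of 70) | 30% (21 of 70) |
| 10% | 10% (7 of 70) | 46.9% (32.8 of 70) | 60% (42 of 70) |

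At 5% per visit, the same six rows fit about 4 to 21 participants. The ratio of highest to lowest is six, the number of injections, at each rate shown. Severity behaves the same way: one severe reaction at every visit may be one participant or six.

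**Denominator.** Section 4.1 makes the analysis set total for the cohort the default denominator, and section 4.2.6.10 states no other. Suppose 7 of 70 react at the first injection, 4 of them stop, and the other 3 react again. The row goes from 7/70 = 10% to 3/70 = 4.3%. The four who stopped are counted as unaffected at visits they did not have.

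**The case against.** The strongest reply is that participant-level information exists elsewhere. For reactions recorded as AEs, section 4.2.6.1 gives participant counts, maximum intensity and a listing. Reactions that end treatment have an AESI table, and AEs leading to discontinuation have their own tables and listing. Whether each graded reaction is also an AE is a recording rule commonly left to the protocol, which is not at hand. This stands in part. A reader might infer that no planned output at all gives participants ever affected, and the SAP does not support that. It supports the narrower statement about the structured assessments.

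A reader might also put orthostatic hypotension on the same footing. The SAP does not support that either. The retained listing shows every participant with a confirmed or symptomatic episode, so those can be counted. Its categories are not severity grades, so worst severity does not apply. What is missing is a per-arm row, plus any across-visit count of those who met the criteria without being confirmed or symptomatic.

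A third tempting reading is that by-visit rates are taken over a shrinking number at risk, so that the example would show 3/66 = 4.5%. The default denominator makes it 3/70. The participants in that example are also those best captured by the discontinuation outputs.

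Finally, safety summaries are descriptive, section 4.2.6 allows further unspecified summaries, and table layouts sit in a separate shells file. An overall row is therefore not excluded, but none is promised.

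**Conclusion.** The point holds for the structured injection-site assessments. They are summarised only by visit, their listing is removed on a ground that does not fit, and no specified output of these data gives participants ever affected or worst severity per arm. AE and AESI outputs fill the gap only as far as reactions are recorded as AEs, and the SAP leaves that extent open.

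The illustrated range of about 4 to 21 of 70 rests on an assumed 5% at each injection, equal arms of about 70 and full attendance. The per-visit rates are not from the SAP. That by-visit rates alone do not settle the participant count does not depend on the rate chosen.

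This is a cheap improvement to safety reporting. It does not touch the primary analysis or the testing strategy. For orthostatic hypotension only a small convenience is missing.

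**What to change.** In section 4.2.6.10, add for each reaction type and arm a row for any post-dose assessment, counting each participant once at worst severity (or presence, for ulceration). Restore the listing of participants with any reaction and amend the matching item in section 6.

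Optionally, in section 4.2.6.5 add a per-arm row for any post-baseline visit for each orthostatic hypotension category, counting each participant once.

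The cost is a few extra table rows and one listing, all from data already collected.

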#### **4.2.6.11 Survey of Autonomic Symptoms (SAS)**

The SAS scores will be summarised by treatment group for the total number of symptoms reported and the total impact score. The summary will be presented by visit and will include the change from baseline.

#### **4.2.6.12 X-ray and MRI**

Summary table suggestive of abnormal findings for each treatment group at the protocol defined visits will be produced.

All data of assessable imaging will be listed for each participant. In addition, a separate listing of participants whose data was sent for adjudication will be produced presenting the outcome of the adjudication review.

#### **4.2.7 Treatment exposure and compliance**

The following summaries related to study treatment will be produced using the safety analysis set by actual treatment group and MEDI7352 Total:

- Participants who received an IP dose
- Maximum number of doses received
  - Participant will be included only in one category depending on the maximum number of doses received during the treatment period. That is if a participant receives only 4 doses during treatment, then this participant should be counted only once in the category '4'
- Duration of exposure as defined in section [3.6.11.1](#)
- Number of participants with dose delay/interruption as reported on the eCRF
- Reasons for dose delays/interruptions as reported on the eCRF
- Cumulative exposure over time (in form of a graph) using the total treatment duration variable as defined in section [3.6.11.1](#).
- Compliance

Administration of study treatment will also be listed for all participants in the safety analysis set. In addition, overdose cases, as reported by the investigator, will be listed. Also, the kit details of the study treatment that were administered will be listed.

#### **4.2.8 Demographic and baseline characteristics**

Disposition, demographic data, and other baseline characteristics will be presented for participants in the FAS (unless otherwise specified below). No statistical testing will be carried out for demographic or other baseline characteristics. The following data will be summarized:

- Participant disposition (Screening set) namely:
  - Enrolled (number of participants only)
  - Rescreened (number of participants only)
  - Randomised/not randomised (including reason)
  - Received study treatment/did not receive study treatment (including reasons)
  - Completed study treatment/discontinued study treatment (including reasons)
  - Completed study/withdrawn from study (including reasons)

Percentages will be based on the randomised participants.

A listing will provide details on participants who were withdrawn from the study and participants who were enrolled and were not randomised. Also, a listing will report participants who completed the study as well as the randomisation codes of all randomised participants.

- Inclusion in analysis sets

A listing will provide the reasons for exclusion from the analysis sets and the participant status for each of the analysis sets.

- Screen failure reasons
  - Number and percentage of participants that did not meet specific inclusion/exclusion criteria

In addition, a listing will provide the reason(s) for screen failures (inclusion/exclusion criteria not met), including rescreened participants.

- Demographics namely:
  - Age (years) at the time of randomisation (derived)
  - Age groups (<65 and >=65)

- Sex
  - Childbearing potential presented for females
  - Reasons for not of childbearing potential included
- Race
- Ethnic group
- Country
- Participant characteristics at baseline namely:
  - Height (cm)
  - Weight (kg)
  - Body mass index (BMI) (kg/m^2)
  - BMI group (kg/m^2) (<18.5, >=18.5 - < 25, >=25 - < 30, >=30)
- Participant recruitment by region, country, and site
- Medical history and surgical history (as appropriate)
  - All medical/surgical history will be classified according to the latest version of the Medical Dictionary for Regulatory Activities (MedDRA).
  - The number (%) of participants with any medical/surgical history (records) will be tabulated by MedDRA system organ class (SOC) and PT. A participant will only be counted once within a particular SOC/PT, regardless of multiple conditions/diseases/surgeries in the same SOC/PT. SOC and PT will be presented in alphabetical order.
- All prior/concomitant medications will be coded using the latest World Health Organization (WHO) Drug Global B3-format dictionary.

Summary tables of allowed and prohibited concomitant medications will present the number (%) of participants, using at least one medication by generic term within anatomical therapeutic chemical (ATC) classification. Participants will be counted once at each level of summarisation (ATC classification/generic term).

- OA related medical history, as collected in the OA medical history eCRF form, namely:
  - Duration of OA (years)
    - Calculated as: Randomization date - OA start date (collected on the OA medical history form), presented in years.
  - Duration of target knee pain (years)

- Calculated as: Randomization date - target knee pain start date (collected on the OA medical history form), presented in years.
- Target knee (left/right), n (%)
  - As collected on the OA medical history form.
- Baseline KL grade
  - As reported by Bioclinica
- Baseline pain intensity score (NRS)
  - As collected in the eDiary

In addition, disease-related treatment at screening will be summarised and will include:

- Previous/ongoing treatments
  - Nonsteroidal anti-inflammatory drugs (NSAIDs)/cyclooxygenase-2 (COX-2) inhibitors
  - Paracetamol
  - Opioids

Pain relief history evaluated in terms of:

- Not effective
- Intolerability
- Contraindication
- No access to opioids (only for opioids)
- Unwillingness to take opioids (only for opioids)

The number (%) of participants will be presented.

- Rescue medication variables defined in section 3.5.1.7 will be summarised by periods as defined in section 3.1.6.

Demographic and baseline characteristics data will also be listed.

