**Table 1 Analysis sets**

Analysis set	Definition
Screening set	All participants who provide informed consent and provide demographic and/or baseline screening assessments, regardless of the participant's randomisation and treatment status in the study. This set will be used for participants' disposition.

---

Analysis set	Definition
Full analysis set	All randomised participants. Participants will be analysed according to the intent-to-treat principle whereby their randomised study treatment will be analysed regardless of the study treatment actually received. This set will be used for demographics and other baseline characteristics, medication description and all efficacy analyses.
Safety analysis set	All participants who received at least one dose of double-blind study treatment. Participants will be analysed according to their actual study treatment received, regardless of the randomised study treatment. This set will be used for safety analyses.
PK analysis set	All participants who received at least one dose of double-blind study treatment per the protocol for whom any post-baseline PK data are available and who do not violate or deviate from the protocol in ways that would significantly affect the PK analyses. Participants will be analysed according to their actual study treatment received, regardless of the randomised study treatment.

---

PK, pharmacokinetics.

The assignment of actual treatment if an incorrect IP is administered will follow the below criteria:

- If a participant randomised to placebo receives at least one dose of MEDI7352 XX mg during the entire double-blind treatment period then the actual treatment arm = MEDI7352 XX, where XX corresponds to the lowest dose of MEDI7352 that participant received during the double-blind treatment period.
- If a participant took only MEDI7352 XX mg treatment during the entire double-blind treatment period, then the actual treatment arm = MEDI7352 XX, where XX corresponds to the dose of MEDI7352 that participant took during the entire double-blind treatment period regardless of what treatment participant was randomized to.
- If a participant took a mix of MEDI7352 XX mg treatments during the entire double-blind treatment period, then the actual treatment arm = MEDI7352 XX, where XX corresponds to the lowest dose of MEDI7352 that participant received during the double-blind treatment period regardless of what treatment participant was randomized to.

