### 3.1.6.3 Post treatment

Post treatment is defined from last IP+15 days through to the date of last study assessment.

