### 3.5.1.7 Rescue medication use

Rescue medication (paracetamol) use will be collected via the participant eDiary from Day -14 until Week 18. Participants who discontinue IP early, will stop recording rescue medication after the ET visit.

The following variables will be derived and/or summarised:

- Number of participants using the rescue medication
- Reason for using rescue medication
- Total number of days rescue medication was used
  - Each day on which rescue medication was used at least once is counted
- Cumulative consumption (mg) of rescue medication use
  - Calculated as the total dose of rescue medication (mg)
- Average daily dose (mg) of rescue medication use
  - Calculated as: cumulative consumption of rescue medication (mg) /total number of days rescue medication was used

In addition to the above and in order to evaluate the changes in rescue medication use (number of days and cumulative consumption) over time, the daily collected data will be assigned to a specific study week. This assignment will use the same principles as deriving the NRS pain scores. For details refer to the section [3.2](#).

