## 4.1 General principles

Efficacy outputs will be presented by cohorts also referred to as the treatment arms, while safety outputs will also include ‘MEDI7352 Total’ defined as the sum of all MEDI7352 cohorts. Study population outputs will be presented by cohorts, MEDI7352 Total and Total (defined as all MEDI7352 cohorts + placebo), except otherwise specified.

The below mentioned general principles will be followed throughout the study:

- Descriptive statistics will be used for all variables, as appropriate, and will be presented by cohort. Continuous variables will be summarised by the number of observations, mean, standard deviation (SD), median, minimum, and maximum. Categorical variables will be summarised by frequency counts and percentages for each category.
- Unless otherwise stated, percentages will be calculated out of the analysis set total for the corresponding cohort.
- For continuous data, the mean and median will be rounded to 1 additional decimal place compared to the original data. The SD will be rounded to 2 additional decimal places compared to the original data. Minimum and maximum will be displayed with the same accuracy as the original data unless otherwise stated.
- For categorical data, percentages will be rounded to 1 decimal place.
- Results of all statistical analysis will be presented using a 95% confidence interval (CI) and 1-sided p-value, unless otherwise stated.
- P-values will be rounded to 3 decimal places, except p-values less than 0.0005 (e.g. 0.0002) will be displayed as <0.001. P-values outputted as <0.0001 by statistical software will not be modified, hence displayed as ‘<0.0001’.
- SAS® version 9.4 or higher will be used for all analyses.

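### In the by-period rescue-medication summary, the default denominator includes participants with no diary in the period, so the post-treatment percentage of users is understated (minor, descriptive table only)

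*SAP*

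**What the plan says.** Section 4.2.8 of the SAP plans this summary: "Rescue medication variables defined in section 3.5.1.7 will be summarised by periods as defined in section 3.1.6". Section 3.5.1.7 lists the variables. The first is "Number of participants using the rescue medication". The others include total days of use, cumulative mg, and an average daily dose defined as cumulative mg divided by the number of days on which rescue medication was used.

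Three general rules settle the denominator when nothing else is stated:

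- Section 4.1 presents categorical variables as counts and percentages, and adds: "Unless otherwise stated, percentages will be calculated out of the analysis set total for the corresponding cohort".
- Section 4.2.8 opens with: "Disposition, demographic data, and other baseline characteristics will be presented for participants in the FAS (unless otherwise specified below". The rescue-medication item names no other set.
- Table 1 defines the full analysis set (FAS) as "All randomised participants" and includes medication description among its uses.

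On recording, section 3.5.1.7 says: "Rescue medication (paracetamol) use will be collected via the participant eDiary from Day -14 until Week 18". It continues: "Participants who discontinue IP early, will stop recording rescue medication after the ET visit". Section 3.1.6.3 sets the period: "Post treatment is defined from last IP+15 days through to the date of last study assessment".

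**The concern.** The period being summarised and the time over which data are recorded do not match. Section 1.2 asks a participant who stops treatment early to attend the ET visit as soon as possible and then to enter follow-up. If that visit falls within 14 days of the last dose, the participant has a post-treatment period but no diary day in it. Under the defaults this person adds one to the denominator and can never add one to the numerator. In the table, an absence of data looks the same as an absence of use.

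Rescue use helps a reader judge a pain comparison, and discontinuation is itself related to outcome here: lack of efficacy is one of the named intercurrent events. A percentage that falls as discontinuation rises can therefore mislead. The totals have a related weakness, because they grow with the number of days recorded as well as with the rate of use.

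**Working it through.** The SAP gives no rescue-medication percentage, so there is no stated figure to reproduce. The check is of what the rules produce.

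**Inputs.** From the SAP: FAS denominator by default (4.1, 4.2.8, Table 1); diary ends after ET for early discontinuers and at Week 18 otherwise (3.5.1.7); post treatment starts at last dose + 15 days (3.1.6.3); dosing every 2 weeks from Day 1 to Week 10 (1.2). Assumed, because the SAP does not give them: u, the proportion using rescue among participants with a diary in the period, and d, the proportion of the FAS with no diary day in the period.

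**Percentage of users.** With N in the FAS, N(1-d) are observed and uN(1-d) are counted as users.

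- FAS denominator: uN(1-d)/N = u(1-d).
- Diary-contributing denominator: uN(1-d)/[N(1-d)] = u.

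At u = 60%:

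| d | FAS denominator | Diary denominator |
|---|---|---|
| 10% | 54.0% | 60.0% |
| 15% | 51.0% | 60.0% |
| 27% | 43.8% | 60.0% |
| 40% | 36.0% | 60.0% |

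The shortfall is u × d. It runs from 3 points (30% × 10%) to 32 points (80% × 40%) over u from 30% to 80% and d from 10% to 40%.

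**Between arms.** With equal use of 60% and d of 15% and 27%, the arms show 51.0% and 43.8%, a spurious gap of 7.2 points. With use of 40% and d = 15%, one arm shows 40% × 0.85 = 34.0%. With use of 50% and d = 27%, the other shows 50% × 0.73 = 36.5%. In that second case the arm with more unobserved participants still looks worse, although the gap shrinks from 10 to 2.5 points. Use that is 0.85/0.73 = 1.16 times higher in the arm with 27% unobserved cancels the artefact.

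**What a new denominator cannot do.** If the unobserved use rescue at rate v, true use in the FAS is u(1-d) + vd. With u = 60%, d = 27% and v = 80%, that is 43.8% + 21.6% = 65.4%. The FAS denominator shows 43.8% and the diary denominator 60.0%. The denominator artefact has gone, but selection from heavier users leaving remains.

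**Totals.** At a constant rate r of use per day, total days of use are r times the days recorded. A participant with only the first dose has at most 15 on-treatment days (Day 1 to Day 15). One with all six doses has 85 (last dose on Day 71, plus 14). At the same rate the totals differ by 85/15 = 5.7 times. After treatment, a completer records about 42 days (Day 86 to Day 127), and an early discontinuer few or none. The average daily dose does not correct for this: it describes the dose on days of use, not use per day recorded.

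**The case against.** The strongest reply is that the FAS denominator is inferred from defaults and never written for rescue medication. Section 3.1.1 says that variables other than the primary and key secondary ones are summarised from available data only, and table layouts are left to shells that are not shown. The SAP nowhere says that a participant without a diary is a non-user. That last point stands: the effect arises from the arithmetic, not from a declared rule. But the available-data rule says which data enter, not what they are divided by, and section 4.1 does say the latter. The SAP makes explicit exceptions elsewhere: liver-test percentages use participants with a measurement (4.2.6.4.1), and the ADA categories use evaluable participants (4.2.5). It makes none here.

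Three stronger readings are tempting, and the SAP does not support them:

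- *The Week 18 percentage has the same fault.* Section 4.2.3 names no percentage for the by-week table, section 3.5.1.7 names days and mg as the variables followed over time, and section 6 calls for available data at protocol visits.
- *The arm with most dropouts will look best.* This holds only when observed use is similar across arms.
- *The percentages shrink to 255/350 = 0.73 of their value.* In section 1.3, 255 is a statistical-information target in a recruitment stopping rule, not a completion rate. Nor does every discontinuer lack post-treatment diary days: an ET visit 15 or more days after the last dose can leave some.

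It is also fair to say that discontinuations are tabulated by reason, so a reader could see differential dropout, and that excessive rescue use enters the primary estimand through separate rules.

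**Conclusion.** The point holds for the by-period summary in section 4.2.8. On the stated defaults, the post-treatment percentage of users is lower than use among those observed by u × d: 9.0 points (60% to 51.0%) or 16.2 points (60% to 43.8%) at the assumed 60% use with 15% or 27% unobserved. These sizes rest on assumed values of u and d; the SAP supplies neither. The direction of any difference created between arms cannot be stated in advance. The period totals depend on recording length, and the average daily dose does not adjust for it.

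The severity is minor. The summary is descriptive, with no test or decision rule attached to it.

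**What to change.** In section 4.2.8 (or 3.5.1.7), state that for each period:

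1. the denominator for the number of users is participants with at least one rescue-diary day in that period, and this n is shown by arm;
2. the post-treatment rescue summary ends at the participant's last diary day, Week 18 at the latest, and is labelled so;
3. days of use and mg are also given per recorded diary day, next to the totals.

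Add a footnote that participants who stopped the diary at ET are not represented after that visit, so selection from heavier users leaving is not removed. The cost is a few lines of SAP text and a table-shell footnote. The diary dates are already collected, and no other analysis changes.
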